6.2 ADHERENCE

Adherence to the dietary recommendations will also be assessed by diet diaries. Eighteen daily diet diaries, in addition to the three diaries at baseline and at 12 weeks, will be undertaken over the 12-week intervention, as identified in **Table 1**.

Table 1:

Scheduled diet diary recording to measure compliance.

	Monday	Tuesday	Wednesday	Thursday	Friday	Saturday	Sunday
Baseline	DD	*	DD	*	*	DD	*
Intervention provided							
Week 1	DD			DD			DD
Week 2			DD			DD	
Week 3		DD			DD		
Week 4	DD			DD			DD
Week 5				DD			
Week 6			DD				
Week 7		DD					
Week 8	DD						DD
Week 9						DD	
Week 10					DD		
Week 11				DD			
Week 12	DD		DD			DD	

DD = Diet diary, including perceived adherence questions

Adherence will be classified five times across the 12-week intervention. During the first two weeks of the trial, adherence will be based on participant ability to reduce free sugars by $\geq 2\%$ TEI from baseline or not, classified as 'adherent' or 'non-adherent' respectively. Participants will then be classified at weeks 4, 8 and 12 using data on their ability to reduce

free sugars by $\geq 2\%$ TEI from previous assessment (baseline for week 4), and their answers to the following adherence question: 'Are you currently following the dietary recommendations you were given?' Reductions of free sugar intakes $\geq 2\%$ TEI and an answer 'YES' will result in a classification of 'active adherent', reductions of free sugar intakes $\geq 2\%$ TEI and an answer 'NO' will result in a classification of 'passive adherent', reductions of free sugar intakes $< 2\%$ TEI and an answer 'NO' will result in a classification of 'active non-adherent', and reductions of free sugar intakes $< 2\%$ TEI and an answer 'YES' will result in a classification of 'passive non-adherent'.

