This updated data from CSV2 was copied into a new file named CSV4. In CSV4 a helper column combining the participants ID number and log day (eg: JS19900.1, combination of JS1990 and 0.1) was used in combination with a new sheet to summarise all nutrients for each participant and each diet diary day. This resulted in 5120 unique daily totals across all nutrients. The CSV4 file was then saved as complete. Including all participants and screened non-participants a total of 70747 individual diary entries on the study via Nutritics Libro. Of these data, 67546 were participant entries and 3201 from non-participant screening diaries, with a total of 10757 unique food items logged.

Sweetener and sweet food counts

Foods that contained sweeteners, were high, medium or low in sugar were separated into counts for each diet diary. These counts were then added into 5 separate scores for the summation of foods consumed in each category for baseline, timepoints 1-4 and endpoint.

ALL DATA - MULTIPLE IMPUTATION

Main analyses were completed on an intention to treat basis as the gold standard for representing the applicability of the intervention in a real world setting rather than an ideal outcome. A variety of techniques to replace/analyse RCT results with missing data have been previously utilised including complete case analysis (CCA), single imputation (SI)(by last observation carried forward, mean or regression), multiple imputation or mixed-effect models (Bell et al., 2014; Li & Stuart, 2019; Ren et al., 2022). CCA and SI methods were discounted due to CCA not being reflective of real-world data, reducing statistical power and SI lacking uncertainty and most likely underestimating variance.

Instructions for the steps used to complete MI and the imputation sequence are included below. As multiple imputation is completed in the order of the variables within the analysis, the variables list was set as randomisation variables first, then nutrient values, anthropometrics and finally questionnaire data in the order that they were completed. All baseline variables were used as predictors, all endpoint variables used as imputations only due to the monotonic pattern.

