Current literature suggests the optimal number of imputations varies between 5-20, with limited benefit over 5. Additional literature supports the number of imputations matching the percentage of attrition. Therefore, the number of imputations for the main analyses was set at 20 representing both the upper recommendation and percentage attrition.

Updates to SPSS now allow random selection of the closest of over >1 donor. Existing methodology and the amount of imputations suggest imputations via Predictive Mean Modelling are selected from the 5 closest donors making this more statistically robust than previous methods.

Before completing multiple imputation, the pattern of missing data was checked. Endpoint data presented as missing in a monotonic pattern. When imputing missing data values in SPSS the custom 'fully conditional specification (FCS)' in methods was selected over monotone. This was because FCS is suitable for both monotone and non-monotone patterned data and introduces Bayesian stochastic regression imputation as part of the predictive means multiple imputation methods. The benefit of this method results in imputed data being taken from both a donor and then adjusted to introduce a level of variability rather than just a copied result. Maximum iterations were set as 50 with FCS convergence checked post imputation. For all applicable statistical tests, analyses were run on each imputed dataset, with values pooled post analysis. This is because a pooled dataset prior to analysis does not just represent the average but retains the variability of the individual imputed datasets.

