Where SPSS did not automatically pool results, Rubin's Rules for combining single estimates were used. The same multiple imputation guidelines were used for the basis for the imputation of all missing data. Where variables presented as having missing data, they were set as 'impute only' to ensure all predictor variables were not based on imputed data. The only difference was in one baseline waist circumference value that was missing in the original data and used in the 2nd MI predictors of the subsequent variables. This study took the premise of not generating imputations based on imputed data values. The same multiple imputation model was run for the initial analyses, adherence and variables completed by only lab participants. Multiple imputation for the adherence data used the same methods and predictors as for the main data set. The step by step methods used are included below. Adherence data points of each free sugar intake at each dietary data point were not included as predictors due to the fact that at least 1 time point needed to be imputed at each variable time point.

Instructions for multiple imputation in SPSS

1. Go to transform – random number generator. Select and set the active generator initialization at a fixed value of 950.
 - a. (This step is to provide a starting point/seed for the MI to enable results to be reproduced)
2. Then Analyze – multiple imputation – impute missing data values.
 - a. Variables tab
 - i. Input all variables for the model in the order they are to be used (this can be found in the output document and also to summarise at the end of this doc) but is all endpoint and corresponding baseline variables, therefore excluding demographics. But including gender. (The order is central for reproducing)
 - ii. Create a new data set – name ComA1_Impu
 - iii. Change imputations to 20
 - b. Method tab
 - i. Custom – select fully conditional specification (set to 50 iterations)
 - ii. Model type – change to PMM – chose from 5 closest (as is default)
 - c. Constraints tab
 - i. Scan data
 - ii. Under define constraints – set all Endpoint variables as impute only.
 1. Instead of clicking use tab and I, plus directional keys to change this.
 - d. Output tab
 - i. Tick imputation model, descriptive statistics and create iteration history – name ComA1_iter
 - e. Double check – click ok
3. Save the imputed and iterations files.

Sequence for multiple imputation.

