BLNFS, BLDGendermale1female2, BLBMI, BLNEnergykcal, BLNCarbohydrateg, BLNProteing, BLNFatg, BLN Sugarsg, BLNFreeSugarsg, BLNFibreg, BLNSaturatedFatg, BLSSodiumNamg, BLWeightkg, BLWaistcircumferencecm, BLLTEShealthscore, BLFCQ1Health, BLFCQ2Mood, BLFCQ3Convenience, BLFCQ4SensoryAppeal, BLFCQ5NaturalContent, BLFC1Q6Price, BLFCQ7WeightControl, BLFCQ8Familiarity, BLFCQ19EthicalConcern, BLSQPC1Personalimpact, BLSQPC2Personalmanagement, BLSQPC3Nonchalance, BLSQPC4Negativity, BLSQPC5Perceivedunderstanding, BLSQPC6PerceivedNonautonomy, BLSF36PCS, BLSF36MCS, BLTSEQ CR, BLTSEQQUE, BLTSEQEE. *Followed by imputation only variables

Get pooled descriptives for analysis / comparison to my values.

1. Data - Split file
 - a. Click split file in ComA1_imp
 - b. Click compare groups
 - c. By imputation number_variable
 - d. Ok
2. Analyze – Descriptive statistics
 - a. Descriptives
 - b. Input all BL and EP variables apart from BL OG FS%.
 - c. Scroll to bottom of output table for pooled means – SD will be calculated from average of 20 imputations at a later date and are not shown here.

BLINDING

The main researcher had no knowledge of allocated groups of participants and was blinded during all data handling and imputation.

DATA ANALYSIS

Outcomes

Primary outcomes were % TEI from free sugars (%FS), and adherence to the recommendations at 12 weeks. Secondary outcomes were dietary profiles (daily energy intake, dietary composition, food consumption), anthropometry, sweet food perceptions and preferences, sweet food choice, attitudes to sweet foods, attitudes towards eating behaviour, motives for food choice, knowledge and lifestyle variables, quality of life and adverse events at week 12; change between baseline and week 12 in key outcomes (%FS, daily energy intake, sugar-sweetened and sweetener-sweetened food consumption, anthropometry), %FS, adherence, dietary profiles and barriers and facilitators towards intervention adherence and success/failure in achieving the recommendations (subset only) at weeks 1, 2, 4 and 8. Demographic variables, and sweet taste sensitivity, sweet liker status and PROP (bitter taste) status were also assessed at baseline, to aid in the interpretation of all outcomes, considering associations between these variables and sweet taste perceptions, liking and food intakes (Jayasinghe et al., 2017; Yeomans et al., 2009).

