Primary models will include gender, age, control/intervention group, baseline %FS, baseline body weight (as randomization variables), and baseline variable of interest. In analyses for %FS, sugar-sweetened food intake, LCS-sweetened food intake, body weight and waist circumference, TEI at Week 12 and physical activity at Week 12 will also be included. Secondary models will also include any additional variable that correlates with each outcome when assessed independently. All variables measured will be considered as secondary variables. Effects for all continuous variables will be investigated using linear multiple regression. Effects for adherence will be investigated using logistic regression to predict adherent vs not adherent.

Analyses Two: Quantitative Data

For analyses two, analyses one will be repeated for demographic groups where significant associations for these variables were found in analyses one. Analyses will only be conducted if significant associations are reported. If no significant associations with demographic variables are found, these analyses will not be completed. These analyses are intended to demonstrate differing effects of the intervention/s in different population groups.

Analyses Three: Qualitative Data

Analyses three will investigate the qualitative data collected from a subset of participants using solo interviews. These interviews were scheduled for completion in a sample of 80 participants from different intervention groups and at different time points. These analyses will be undertaken using a thematic framework analysis. First, a random sample of interviews will be analysed inductively using thematic analysis to identify codes. These codes will be used to create a framework and the framework then applied to all interviews.

Framework analysis has been chosen as a suitable analytical method for evaluating the qualitative interview data gathered, due to an interest in individual experiences and seeks to identify the different factors (barriers or facilitators) that contributed to successful or unsuccessful dietary change (Braun & Clark, 2013). The practical methods for conducting framework analysis follow a methodology as outlined below.

Framework analysis (Braun & Clarke, 2006; 2013; Gale et al, 2013).

Phase 1 'Familiarizing yourself: Transcribing data (if necessary), reading and re-reading the data, noting down with your data: initial ideas'.

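### Leavers' week-12 adherence and %FS are imputed from stayers similar at baseline, ignoring arm and on-trial intake, and no analysis tests the assumption that leavers resemble stayers

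*SAP*

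**What the plan says.** The SAP (Outcomes) names two primary outcomes: "Primary outcomes were % TEI from free sugars (%FS), and adherence to the recommendations at 12 weeks". Its multiple imputation section defends an intention-to-treat analysis as "representing the applicability of the intervention in a real world setting rather than an ideal outcome". It sets aside complete-case analysis and single imputation.

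Missing values are filled by predictive mean matching: "Predictive Mean Modelling are selected from the 5 closest donors". On predictors it says: "All baseline variables were used as predictors, all endpoint variables used as imputations only due to the monotonic pattern". For adherence, "Multiple imputation for the adherence data used the same methods and predictors as for the main data set". Free sugar intakes at the diary time points "were not included as predictors due to the fact that at least 1 time point needed to be imputed". The listed imputation sequence opens with baseline %FS, gender and BMI, runs through other baseline measures, and does not contain trial arm. The Blinding section says the main researcher did not know allocations while imputing.

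Protocol 7.4 defines withdrawal as saying so or not attending the final test day. Protocol 6.2 measures following the advice separately. At weeks 4, 8 and 12 it combines a free sugar reduction criterion with the question "Are you currently following the dietary recommendations you were given". The SAP (Analyses One) then states: "Effects for adherence will be investigated using logistic regression to predict adherent vs not adherent".

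Neither document says how withdrawal counts towards adherence. The available text describes no analysis of either primary outcome under a different missing-data assumption.

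**The concern.** The trial asks whether people act on advice. A leaver's missing result is drawn from people who stayed and looked similar at baseline. What the leaver's own diaries showed before leaving is not used, nor is the arm they were in. Under this model, uneven leaving cannot count against an advice arm.

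That sits uneasily with a stated real-world aim. Whether leavers resemble stayers cannot be checked for people with no week-12 data, and about a fifth of the results on both primary outcomes depend on it. A reader of the trial report could not tell whether the conclusion rests on that assumption.

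**Working it through.** **Inputs from the documents**
- N = 242 (SAP, Data presentation).
- Attrition of about 20%: the SAP sets 20 imputations partly to match percentage attrition, and Protocol 4.2 allows 20%. Attrition by arm is not given.
- Four arms, planned equal (Protocol 4.2).
- Donors are participants with observed values; arm is not in the listed predictors.

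Results imputed at week 12: 0.20 × 242 = 48.4, about 48 participants.

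**Assumptions, because the documents give no figures**
- Adherence among completers is p_A = 0.50 in each of the three advice arms and p_C = 0.30 in control.
- Attrition is m_A in each advice arm and m_C in control.
- Randomisation balances the baseline predictors, so a leaver's donors come from the completers of all four arms in proportion.

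**Formulas**
- Donor pool rate: q = [3(1 − m_A)p_A + (1 − m_C)p_C] / [3(1 − m_A) + (1 − m_C)]
- Listed imputation, each arm: (1 − m)p + m·q
- Leaver counted as not adherent, each arm: (1 − m)p
- Gap between the two differences: q(m_A − m_C), which is zero when attrition is equal

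**Donor pool**
- 20/20: q = (3 × 0.80 × 0.50 + 0.80 × 0.30) / 3.20 = 1.44 / 3.20 = 0.450
- 25/15: q = (3 × 0.75 × 0.50 + 0.85 × 0.30) / 3.10 = 1.38 / 3.10 = 0.445
- 30/10: q = (3 × 0.70 × 0.50 + 0.90 × 0.30) / 3.00 = 1.32 / 3.00 = 0.440

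**Results**

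| Attrition, advice/control | Listed imputation, advice vs control | Difference (points) | Leaver not adherent, advice vs control | Difference (points) | Gap (points) |
|---|---|---|---|---|---|
| 20/20% | 49.0% vs 33.0% | 16.0 | 40.0% vs 24.0% | 16.0 | 0 |
| 25/15% | 48.6% vs 32.2% | 16.5 | 37.5% vs 25.5% | 12.0 | 4.5 |
| 30/10% | 48.2% vs 31.4% | 16.8 | 35.0% vs 27.0% | 8.0 | 8.8 |

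The last two rows imply overall attrition of 22.5% and 25%. A split that keeps 20% overall is 25/5%. There q = 1.41 / 3.20 = 0.441, the listed imputation gives 48.5% vs 30.7% (17.8 points), and the alternative gives 37.5% vs 28.5% (9.0 points).

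**No difference among completers** (assumed 40% in every arm, attrition 25/5%): the listed imputation gives 0. Counting leavers as not adherent gives 0.75 × 0.40 − 0.95 × 0.40 = 0.30 − 0.38 = −8 points.

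These are expected proportions, not simulations of the full imputation model. The same donor rule applies to %FS, but the documents give no figures from which to size the effect there.

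**The case against.** Three readings go further than the documents allow.

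- **A reader might infer that the imputed result treats everyone as continuing to follow the advice.** It does not. Donors include people who stayed and were not adherent, or who answered no to the adherence question. The most that can be said is that it treats everyone as having stayed in the trial.
- **A reader might take leaving as direct evidence of not following the advice.** Protocol 7.4 and 6.2 keep the two apart. The diary load is heavy in every arm, control participants have no sugar advice to abandon, and someone who misses the final visit may still have week-12 diaries in the app. If leavers do resemble similar stayers, the imputation serves the real-world aim.
- **A reader might assume imputation within arm, which would hold the difference at 20 points (50% − 30%) whatever the attrition.** With arm absent from the listed sequence, donors are pooled and the arms are pulled together, which is why the table starts at 16.

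Other objections also have weight. At weeks 8 and 12 the free sugar criterion is measured from the previous assessment, so someone who merely keeps an early reduction does not meet it. The 50% and 30% rates are therefore only illustrative. The SAP already plans a CONSORT diagram showing completion by group and drop-out, so uneven leaving would not be hidden. Counting leavers as not adherent is itself a deterministic single imputation, a class the SAP rejects, and in control it marks as failures people who were given no advice. Return to baseline is one choice among several.

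These points limit how far an alternative analysis can be trusted as a main result. They do not remove the gap: a drop-out table shows who left but does not test what is assumed about them.

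**Conclusion.** The concern holds in a limited form. Both primary outcomes rest, for about 48 of 242 participants, on the assumption that leavers resemble stayers of any arm with similar baseline values. Collected on-trial intakes are not used as predictors, and no stated analysis shows what happens if the assumption fails.

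Under the assumed rates, the choice of assumption changes the between-arm difference by nothing at equal attrition, by 4.5 points at 25/15% and by 8.8 points at 30/10%. The absolute rate in an advice arm falls in every case, from 49% to 40% at equal attrition. Whether the contrast is affected here depends on attrition by arm, which the documents do not give.

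The main analysis is not invalid, and the documents do not show that it favours advice. The finding is a missing robustness check, together with the absence of arm from the listed imputation model. It rests on the available SAP text. That text does not say whether the adherence class, the yes/no answer or the underlying %FS is what is imputed.

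**What to change.** Keep multiple imputation as the main analysis, with trial arm added to the imputation model. State how withdrawal counts in the adherence outcome, and add one sensitivity analysis per primary outcome:

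1. **Adherence:** participants who withdrew before an assessment and have no diary data for it count as not adherent at that and later assessments.
2. **%FS:** withdrawn participants' missing week-12 values are imputed around their own baseline %FS, with residual variation.

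Report both beside the main result and the drop-out by arm already planned, and say in words whether the conclusion depends on the missing-data assumption. A rule that significance must hold in both analyses is not needed.

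The cost is a re-run of the imputation with arm included, SAP wording, and two extra analyses on data already held. The reported effect may look less favourable. With arm in the model, the main difference in the illustration returns to 20 points, so the gaps to analysis 1 become 4, 8 and 12 points (20 − 16, 20 − 12, 20 − 8). Adding arm needs allocation codes, which someone other than the blinded researcher can supply in coded form. The SAP reports the imputation as already done, so label these analyses as added at that stage if they were not specified before unblinding.

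### Trial arm is left out of the multiple-imputation model, so arm contrasts shrink to about 80% of their true size when 20% of the data are missing

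*SAP*

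**What the plan says.** The imputation model is described in three places in the SAP, and they agree.

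- **All data – multiple imputation:** "All baseline variables were used as predictors, all endpoint variables used as imputations only due to the monotonic pattern".
- **Instructions for multiple imputation in SPSS:** the variable list "is all endpoint and corresponding baseline variables, therefore excluding demographics. But including gender".
- **Sequence for multiple imputation:** the list opens with "BLNFS, BLDGendermale1female2, BLBMI, BLNEnergykcal" and closes with "BLTSEQ CR, BLTSEQQUE, BLTSEQEE. *Followed by imputation only variables". It has 35 entries, all baseline variables. Neither trial arm nor age is among them.

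The text places randomisation variables first. The first three entries are baseline free sugars, gender and BMI, which are the stratifiers in Protocol 4.3, so the phrase does not refer to the allocated arm.

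For the second primary outcome, "Multiple imputation for the adherence data used the same methods and predictors as for the main data set", and "Adherence data points of each free sugar intake at each dietary data point were not included as predictors". The only split-file step is by imputation number, after imputation. The blinding paragraph says the main researcher did not know the allocation while imputing.

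On the amount of missing data, "the number of imputations for the main analyses was set at 20 representing both the upper recommendation and percentage attrition". Protocol 4.2 also allows for 20% attrition. Missingness by arm is not given.

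In Analyses One, "Primary models will include gender, age, control/intervention group", followed by baseline covariates. For free sugars the model also includes week-12 energy intake and physical activity.

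**The concern.** An imputation model should contain every variable whose effect the analysis model estimates. Here the effect of interest is trial arm, and the imputation cannot see it. Arm has no indirect route in either, because no post-randomisation variable is used as a predictor.

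Predictive mean matching then picks donors by baseline profile from all four arms together. Participants with missing data in every arm, control included, receive the same pooled average effect. The completed data mix real outcomes, which carry the arm difference, with imputed outcomes, which do not. This feeds the main intention-to-treat analysis of both primary outcomes, and contrasts between intervention arms shrink as well as contrasts with control.

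**Working it through.** **Inputs.** From Protocol 4.2: target difference 2% TEI and standardised difference 0.8, so SD = 2/0.8 = 2.5; 60 per arm less 20% leaves 48 completers per arm. From the SAP: N = 242, f about 0.20, 20 imputations, 5 donors. The plan gives no figure for the imputed contrast, so there is none to reproduce.

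**Closed form.** Take the control mean as 0, let arm *a* have effect *e*, and let *p* be the mean effect over completers of all arms. After imputation without arm, the expected mean is (1 − f_a)·e + f_a·p in arm *a* and f_c·p in control. The contrast is therefore

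(1 − f_a)·e + (f_a − f_c)·p.

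*Equal attrition.* The second term vanishes and the factor is (1 − f). The simulated ratios are from 400 trials per row (SD 2.5, baseline correlation 0.5 assumed):

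| f | Estimate when truth is −2.0 | Simulated ratio, arm omitted |
|---|---|---|
| 0.10 | −1.8 | 0.89–0.91 |
| 0.20 | −1.6 | 0.78–0.80 |
| 0.30 | −1.4 | 0.70 |

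At f = 0.20 the ratio was 0.77–0.78 when missingness depended on baseline. With arm in the imputation model it was 0.97–1.02.

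*Unequal attrition averaging 20%* (illustrative, all three interventions at −2.0):
- Control 10%, interventions 23.3%: p = −2 × 2.3/3.2 = −1.44. Contrast = 0.767 × (−2) + 0.133 × (−1.44) = −1.73, a shrinkage of 14%.
- Control 30%, interventions 16.7%: p = −2 × 2.5/3.2 = −1.56. Contrast = 0.833 × (−2) + (−0.133) × (−1.56) = −1.46, a shrinkage of 27%.
- Ineffective arm at 30%, control at 10%, two arms at −2.0 with 20% missing: p = −3.2/3.2 = −1.0. Contrast = 0.20 × (−1.0) = −0.2, where the truth is zero.

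**Simulation with the SAP's analysis model.** 800 trials per scenario, 35 baseline predictors, 20% missing depending on baseline free sugars, Rubin's rules. Week-12 energy intake and activity were imputed from baseline only. Assumed: baseline correlation 0.3 to 0.5, predictor correlation 0.2, residual correlation of energy intake with free sugars 0.2.

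| | Arm omitted | Arm and age included |
|---|---|---|
| Estimate when truth is −2.0 | −1.60 to −1.63 | −1.99 to −2.02 |
| Power at −2.0 | 94–98% | 98–100% |
| Power at −1.43 | 64–77% | 79–90% |

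The value 1.43 is the difference that 48 completers per arm detect with 80% power: 2.80 × 2.5 × √(2/48) = 1.43. With arm omitted, coverage was 91–95% at −2.0 and 95–97% at −1.43, and null rejection was 1–2%. The low null rejection fits the standard errors in the 400-trial runs: Rubin's rules gave about 0.46, against an actual spread of about 0.36 to 0.39 at 20% missing.

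**Adherence** (illustrative; the rates are assumed and f is taken as 0.20). With true rates of 30% in control and 50% in each intervention arm, the pooled rate is (30 + 3 × 50)/4 = 45%. Control becomes 0.8 × 30 + 0.2 × 45 = 33%, and intervention becomes 0.8 × 50 + 0.2 × 45 = 49%. The difference falls from 20 to 16 points, and the odds ratio from 2.33 to 1.95.

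**The case against.** The strongest objection is that the shrunken contrast may be the right one. The intervention is a single set of written recommendations with no questions allowed (Protocol 5.1.5), and participants who do not attend the final test day count as withdrawn (7.4). If those participants lose the whole effect and attrition is equal, the true contrast is (1 − f)·e, which is exactly what omission returns at every f. That identity stands. It fails once attrition differs: with control at 10% and interventions at 23.3%, the contrast under full reversion is 0.767 × (−2) = −1.53, while omission gives −1.73. The SAP states no such estimand, and its imputation also assigns the pooled effect to control dropouts.

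Second, the practical harm at the design effect is limited. Power at −2.0 stays at 94% or more and false positives are not inflated under equal attrition. This also stands. The bias in the estimate remains, and power suffers more at smaller true differences, which may be what separates one type of recommendation from another.

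Third, the SAP refers to an output document that is not available, and arm might appear there. But the SAP prints the rule and the sequence so that the imputation can be reproduced, and both omit arm. If arm was used, the SAP must say so.

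Fourth, the researcher was blind while imputing. Blinding calls for masked codes and does not require leaving arm out.

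**Conclusion.** The concern holds. As written, the imputation ignores trial arm, and the primary model then estimates arm effects from the imputed data. Under missing at random with similar attrition in each arm, contrasts are multiplied by (1 − f): about 0.8 at the attrition the SAP implies, or −1.6 in place of −2.0.

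The omission rests on the text alone. The size rests on the missing-at-random assumption and on an overall f of 0.20. Power and coverage also depend on the assumed correlations, and the adherence figures are purely illustrative. The fraction f is not given by arm, for the interim weeks, or for the laboratory-only outcomes, which at-home participants skip (Protocol 7.3), so the factor for those analyses is unknown.

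Age is also in the primary model but absent from the imputation model. That is a lesser mismatch and does not cause the shrinkage. Because both primary outcomes are affected, this should be corrected before results are reported.

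**What to change.** - Add trial arm to the imputation model as a categorical predictor (three indicators) under masked codes A to D, and add age. Imputing separately by arm is not needed, and would be unstable with about 48 completers against 35 predictors.
- To protect the blind, have someone independent run the imputation or withhold its model output, since arm coefficients could let the analyst guess which code is control.
- Report missingness by arm and time point for each primary outcome.
- As a secondary option, allow interim free-sugar values and endpoint variables to act as predictors under the fully conditional specification already chosen, as far as their number and collinearity permit.
- If dropouts are meant to be treated as losing the effect, specify that as a reference-based sensitivity analysis.

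The cost is a few words in the SAP and four added predictor columns. The main, adherence and laboratory-only imputations and their pooled analyses must be repeated. No new data are needed.
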